Table 1. Double-Blind Dose Transition Blister Cards for ≥ 45 kg Subjects on 160 mg/day or 140 mg/day of Active Ziprasidone or Placebo at End of Study A1281198, Weeks 1 and 2	26
Table 2. Double-Blind Dose Transition Blister Cards for ≥ 45 kg Subjects on 120 mg/day of Active Ziprasidone or Placebo at End of Study A1281198, Weeks 1 and 2.....	26
Table 3. Double-Blind Dose Transition Blister Cards for ≥ 45 kg Subjects on 80 mg/day or 100 mg of Active Ziprasidone or Placebo at End of Study A1281198, Weeks 1 and 2	27
Table 4. Double Blind Dose Transition Blister Cards for < 45 kg Subjects on 40 mg/day, 60 mg/day, or 80 mg of Active Ziprasidone or Placebo at End of Study A1281198, Week 1	28
Table 5. 40 mg Fixed Dose Regimen	28
Table 6. 60 mg Fixed Dose Regimen	29
Table 7. 80 mg Fixed Dose Regimen	29
Table 8. 100 mg Fixed Dose Regimen	29
Table 9. 120 mg Fixed Dose Regimen	30
Table 10. 140 mg Fixed Dose Regimen	30
Table 11. 160 mg Fixed Dose Regimen	30
Table 12. Prohibited/Concomitant Medication Table.....	35

APPENDICES

Appendix 1. Abbreviations	73
Appendix 2. Criteria for Training Approval without Sponsor Review	76

PROTOCOL SUMMARY

Indication:

Study A1281201 is a 6-month, open label extension study of the ongoing double-blind, randomized, placebo controlled study of ziprasidone in pediatric Bipolar Disorder (Study A1281198). Study A1281201 will enroll adolescents aged 10 to 17 years with Bipolar I Disorder who have participated in double blind Study A1281198. In order to be enrolled in this open label extension trial, subjects must have met the enrollment criteria for Study A1281198, and must meet the inclusion and exclusion criteria for Study A1281201 at the extension study Baseline visit (last visit in the double blind study).

Rationale:

The purpose of adding this extension study to the ongoing Geodon pediatric bipolar program is to obtain additional longer term safety data in children and adolescents with Bipolar I disorder treated with ziprasidone.

Trial Design:

This 26-week open-label extension study is designed to provide information on the safety and tolerability of oral ziprasidone (20-80 mg BID (twice daily) with meals) during long-term administration in children and adolescents with Bipolar I Disorder (current or most recent episode manic). It will enroll subjects who have participated in the 4-week, double-blind, placebo-controlled safety and efficacy trial, Study A1281198, meet study entry criteria, and wish to receive treatment with open-label ziprasidone.

The final visit of the double-blind trial (Week 4 or early termination) will serve as the Baseline Visit for the extension study. During the first 1-14 days of the study, subjects will be transitioned under double-blind conditions to treatment with open label ziprasidone. The dosing of ziprasidone will be flexible in Weeks 3-26 of this study.

Post-Baseline visits will occur at Weeks 1, 2, 4, 6, 10, 14, 18, 22, 26 during treatment, with a follow-up visit at Week 27.

A telephone call must occur 28 to 35 days from administration of the final dose of investigational product to capture any potential adverse events and to confirm appropriate contraception usage.

Endpoints:

Safety Assessments:

- Adverse event reporting; |
- Clinical laboratory testing;
- Physical examinations;

- Blood pressure and pulse;
- Height and weight;
- Body Mass Index (BMI), BMI Z-score;
- Waist circumference;
- Electrocardiograms, including QT interval corrected for rate (QTc).

Special Safety Assessments:

- Movement Disorder Scales - Simpson Angus Rating Scale (SARS), Barnes Akathisia Rating Scale (BAS), and Abnormal Involuntary Movement Scale(AIMS);
- Columbia Suicide Severity Rating Scale (C-SSRS);
- Child Depression Rating Scale (CDRS- R).

Efficacy Assessments:

- Young Mania Rating Scale;
- Clinical Global Impression of Severity (CGI-S);
- Children's Global Assessment Scale (CGAS).

Trial Treatments:

All investigational products will be provided by Pfizer and will include oral ziprasidone capsules of 20, 40, 60, and 80 mg strength. Matching placebo capsules will also be supplied for the initial 1-14 day dose transition period. All medication will be packaged in childproof blister cards with columns for AM and for PM capsules.

During the dose transition period (Weeks 1-2, Days 1-14), subjects will receive a study drug blister card for each week of transition dosing. Subjects weighing ≥ 45 kg will receive 2 weeks of transition medication, while subjects weighing less than < 45 kg will receive 1 week of transition medication.

At the baseline visit of the A1281201 study, subjects will transition onto active medication if previously assigned to the placebo group or continue on active study drug. Over the course of the double-blind dose transition period, subjects < 45 kg will be transitioned to a total daily dose of 60 mg a day by Day 7 of Week 1 and subjects ≥ 45 kg will be transitioned to a total daily dose of 120 mg a day by Day 10 of Week 2. (Subjects on 160 mg, 140 mg, 100 mg, and 80 mg active at the end of Study A1281198 will all be transitioned to 120 mg a day at the end of the two-week transition period. Subjects on 120 mg active at the end of Study A1281198 will remain on 120 mg a day through the dose transition period).

During the dose transition period, investigators, subjects, and the study team will be kept blinded to the content of the dose transition cards (which contain both placebo and active ziprasidone capsules) but not to the dose level of study medication.

Dose level for each day of the transition dosing card for subjects who were on placebo or ziprasidone in Study A1281198 are provided in [Table 1](#), [Table 2](#), [Table 3](#) and [Table 4](#).

Any subject who cannot tolerate the transition study medication during Week 1 should be discontinued from the study.

After the Week 2 visit for the ≥ 45 kg subjects and after the Week 1 visit for the <45 kg subjects, dosing will be open label and flexible, with dosing adjustments made at the discretion of the investigator to maintain optimal efficacy and tolerability. The target dose range for subjects <45 kg is 60 mg to 80 mg/day and for subjects ≥ 45 kg, 120 mg to 160 mg/day, which are identical to the target dose ranges used in Study A1281198.

The blister cards for Weeks 3-26 will each contain medication for 8 days. Two blister cards will be dispensed at Weeks 2 and 4 and then 4 blister cards will be dispensed at each monthly visit from the Weeks 6 visit through the Week 22 visit. Dose increases should be limited to 20 mg a week during Weeks 6-22 of the flexible dosing weeks of the study. However, subjects ≥ 45 weight can be increased to 160 mg a day after they have been on a stable dose of 120 mg a day if clinically indicated. [Table 1](#), [Table 2](#), [Table 3](#) and [Table 4](#) provide the dose transition schedule for all possible dose levels for subjects in both weight categories.

Statistical Methods:

Sample Size

The number of subjects entering this open-label trial will be determined by the number of subjects electing to continue treatment after completing or withdrawing from the preceding double blind study, A1281198. We estimate that approximately 55 subjects randomized in the double blind study (based on the increased sample size of N (number) =194 subjects) will be eligible to continue in this open label extension. With an expected dropout rate of approximately 35%, this gives an estimate of approximately 40 subjects to complete this 26 week open label study (if all 55 subjects enter the extension study).

Data Summarization Methods

As this is an open label study with no comparator, no inferential statistics will be performed. Quantitative variables will be described by standard descriptive statistics (n, mean, standard deviation, minimum, and maximum, 95% confidence intervals), and qualitative variables will be summarized by frequency tables. Summaries will include data for all subjects who took at least one dose of investigational product in this open label extension study.

Baseline values for efficacy, outcomes and special safety endpoints will be the last observation made prior to the subject's receiving open label treatment. For safety, for those subjects who were randomized to placebo in the double blind study, baseline values will be

the last observation prior to initiating dosing in the open label extension study (normally, the observation of the last visit in the double blind study); and for those subjects who were randomized to ziprasidone in the double blind study, baseline values will be the last observation prior to initiating dosing in the double blind study (normally, the value from the Baseline visit in the double blind study).

Safety data from this trial will be monitored by the independent Data Monitoring Committee (DMC) currently monitoring study A1281198. Details of the board's functions are documented in the DMC Charter.

SCHEDULE OF ACTIVITIES

The schedule of activities table provides an overview of the protocol visits and procedures. Refer to the **STUDY PROCEDURES** and **ASSESSMENTS** sections of the protocol for detailed information on each procedure and assessment required for compliance with the protocol.

The investigator may schedule visits (unplanned visits) in addition to those listed on the schedule of activities table, in order to conduct evaluations or assessments required to protect the well-being of the subject.

Activities/ Assessments	Baseline ^a	Open-label Ziprasidone										Follow up Visit	Follow Up ¹
		± 1 Day					±3 days						
Visit	1	2	3	4	5	6	7	8	9	10	11	12	
Visit Schedule	Day 1	W1	W2	W4	W6	W10	W14	W18	W22	W26/ ET ^a		W27	
Informed Consent, Assent ^c	X												
Inclusion/Exclusion	X												
Physical Exam	X										X		
Body Weight/Height/ BMI/BMI-z score/ waist circumference	X				X						X	X ^d	
ECG ^{*e}	X	X	X	X	X		X		X	X	X	X ^d	
Blood Pressure/Pulse ^f	X	X	X	X	X	X	X	X	X	X	X	X ^d	
Chem/Hemato/Urinalysis	X				X						X	X ^d	
Hormones (free T4 & TSH, Prolactin)	X				X						X	X ^d	
Fasting glucose, lipids, insulin, HbA1c ^{**}	X				X			X			X	X ^d	
Urine drug screen ^g	X				X						X		
Urine Pregnancy Test ^h	X	X	X	X	X	X	X	X	X	X	X	X	
Verification of contraception	X	X	X	X	X	X	X	X	X	X	X	X ⁱ	
Dispense Double-Blind Transition Card ^{j,m}	X	X ^{m,j}											
Dispense Study Drug	X	X	X	X	X	X	X	X	X				
Drug Accountability		X	X	X	X	X	X	X	X	X			
Subject telephone contact ⁱ		X	X			X	X	X	X	X		X ⁱ	
YMRS	X	X	X		X		X		X	X			
CGI-S	X	X	X	X	X	X	X	X	X	X			
CGAS	X										X		
CDRS-R	X	X	X	X	X	X	X	X	X	X	X ^d		
SARS, BAS, AIMS	X	X	X	X	X	X	X	X	X	X	X ^d		
C-SSRS ^k	X	X	X	X	X	X	X	X	X	X	X		
Serious and non-serious adverse event monitoring	X	X	X	X	X	X	X	X	X	X	X	X ⁱ	
Concomitant Medication	X	X	X	X	X	X	X	X	X	X	X	X	

ET = early termination; BMI = Body Mass Index; ECG = Electrocardiogram; T4 = Thyroxin 4; TSH= Thyroid-Stimulating Hormone; HbA1c = glycated hemoglobin; YMRS = Young Mania Rating Scale; CGI-S = Clinical Global Impressions of Severity; CGAS =Children's Global Assessment Scale; CDRS-R = Child Depression Rating Scale - Revised; SARS = Simpson Angus Rating Scale; BAS = Barnes Akathisia Rating Scale; AIMS = Abnormal Involuntary Movement Scale; C-SSRS = Columbia Suicide Severity Rating Scale.

* All ECGs will be administered at least 3 hours after food intake.

** Subjects should remain fasting for at least 8 hours prior to the baseline visit, Week 6, Week 18, and Week 26..

- a. Baseline Visit is the last visit of the preceding double-blind trial, Study A1281198. In the case of early termination, all procedures specified for Week 26/ET are to be completed.
- b. Every effort should be made to bring the subject back to the office on the designated study days; however, monthly office visits will have a ± 3 day visit window to allow for slight variations in subject schedules. When scheduling subsequent visits, the overall treatment period in the protocol should be maintained.
- c. Subjects who turn 18 years old during the study need to give a written consent.
- d. Only if the subject had clinically significant abnormal findings from a previous visit that require follow-up.
- e. ECGs showing a QTcF of >480 msec or a suspected increase from baseline of 60 msec or greater must be repeated within the same visit. If the QTcF value persists at >480 msec and/or the change from baseline persists at >60 msec, the study drug must be discontinued immediately and a pediatric cardiologist or an adult cardiologist experienced in the interpretation of pediatric ECGs should be contacted to discuss the ECG result.
- f. The subject should be in the sitting position for approximately 5 minutes and in the standing position for approximately 2 minutes before the measurements are obtained.
- g. Following the baseline visit, unscheduled urine drug screens can be performed at additional visits at the investigator's discretion.
- h. At all required visits, a urine pregnancy test should be performed followed by a serum pregnancy test if the urine test is positive. A negative pregnancy test is required before the subject may receive investigational product. Unscheduled pregnancy tests can be performed at additional visits at the investigator's discretion. Pregnancy tests should also be done whenever one menstrual cycle is missed during the active treatment period (or when potential pregnancy is otherwise suspected). Pregnancy tests may also be repeated as per request of IRB/IECs or if required by local regulations.
- i. As double blind study medication will be transitioned during the first two weeks of the study for subjects weighing ≥ 45 kg and during the first week of the study for subjects <45 kg, the investigator or designated staff must be in contact with the subject and his/her parent(s) and/or guardian(s) in between the Baseline and Week 1 visit and between the Week 1 and Week 2 visit. After the Week 6 visit, the investigator or designated staff must be in contact with the subject and his/her parent(s) and/or guardian(s) in between study visits by telephone to ensure that the subject is taking the proper capsules at the proper time and to monitor the tolerability and efficacy of the study medication.
- j. Double-Blind Transition Card provided only to ≥ 45 kg weight group subjects.
- k. A risk assessment should be done to determine if it is safe for the subject to participate in the trial or continue to participate in the trial, if the subject's responses during the suicidality assessments indicate that the subject has had suicide ideation associated with actual intent and/or plan or exhibited suicidal behaviors.
- l. Follow up contact will be completed at least 28 calendar days, and up to 35 calendar days after the last administration of the investigational product to capture any potential adverse events (see the [Time Period for Collecting AE/SAE Information](#) section) and to confirm appropriate contraception usage (see the [Contraception](#) section). Contact with the subject may be done via a phone call.
- m. Any subject who cannot tolerate the transition study medication during Week 1 should be discontinued from the study.

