4.2. Exclusion Criteria

Subjects with any of the following characteristics/conditions will not be included in the study:

1. Any subjects from the preceding double blind trial who experienced a serious adverse event which required study medication to be discontinued and the subject to be withdrawn from the study. Subjects who experienced cardiac arrhythmias, conduction abnormalities, or QTc prolongation (confirmed and persistent Fridericia's correction (QTcF) >480 msec or increase from baseline QTcF >60 msec) during the preceding study.
2. Subjects requiring any medications not allowed by the Concomitant Medication [Table 12](#) (see “[Concomitant Treatment\(s\)](#)”).
3. Subjects who require treatment with drugs that are known to consistently prolong the QT interval (see Concomitant Medication [Table 12](#)).
4. Subjects who are judged by the investigator as being at imminent risk of suicide.
5. Subjects living in the same home as another study participant or having the same caregiver during the same enrollment period (Such subjects can be enrolled in the study at different times but may not be in the study at the same time).
6. Subjects should be excluded or a risk assessment should be done to verify that it is safe for the subject to participate in the trial if the subject's responses on the C-SSRS or other information based on the investigator's judgment indicate:
 - Suicide ideation associated with actual intent and a method or plan such that a positive response ('Yes') is made on items 4 or 5 of the suicidal ideation subscale of the C-SSRS; or
 - Any suicide behaviors such that a determination of 'yes' is made to any of the suicide behavior items of the C-SSRS.
7. Pregnant female subjects, breastfeeding female subjects.
8. Participation in other studies other than the preceding Study.
9. Other acute or chronic medical or psychiatric condition including recent (within the past year) or active suicidal ideation or behavior or laboratory abnormality that may increase the risk associated with study participation or investigational product administration or may interfere with the interpretation of study results and, in the judgment of the investigator, would make the subject inappropriate for entry into this study.

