Syncope	All syncopal episodes suggestive of cardiac arrhythmia (sudden loss of consciousness, loss of postural tone, and no pre-syncopal phase), except vasovagal syncope will be considered adverse events and the subject will be discontinued from the study. Every effort should be made to obtain vital signs and an electrocardiogram at the time of the event. Further evaluation, eg, Holter monitoring, may also be useful. Subjects experiencing syncope of probable vasovagal origin (onset not sudden but preceded by a pre-syncopal phase, presence of predisposing factors such as blood sampling procedure, standing, hot shower, hair curling, etc) will also be considered adverse events but subjects may continue study participation after sponsor approval.

Event	Criteria
Prolonged QT	
Electrocardiograms are to be reviewed and compared to baseline to assess potential changes. ECGs showing a QTcF of ≥ 480 msec or a suspected increase from baseline of 60 msec or greater must be repeated within the same visit. If the QTcF value persists at ≥ 480 msec and/or the change from baseline persists at ≥ 60 msec, the study drug must be discontinued immediately and a pediatric cardiologist or an adult cardiologist experienced in the interpretation of pediatric ECGs should be contacted to discuss the ECG result.
 
A verified increase in QTcF of ≥ 60 msec or a verified occurrence of QTcF ≥ 480 msec will be considered as an adverse event of QTc prolongation. QTcB (Bazett's correction) prolongation will not be used to define adverse events; QTcB will be measured only to enable historical comparisons.

Ventricular arrhythmia	
An ECG showing ventricular arrhythmia (except single ventricular extrasystoles) should be followed up with a rhythm strip ECG and Pfizer must be notified. In addition, a stat over read from the central vendor should be requested, a pediatric cardiologist or adult cardiologist experienced in the diagnosis and treatment of pediatric arrhythmias should be consulted, and the subject monitored, as necessary. If the ventricular arrhythmia is confirmed, the subject must be discontinued from the study.

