7.2. Electrocardiograms

A 12-lead ECG will be obtained from each subject at Weeks 1, 2, 4, 6, 14, 22 and Week 26 and repeated at the follow-up visit if abnormalities were present at the Week 26 (or early termination) visit. Baseline ECG data will be obtained from A1281198 final study visit.

The subject must fast at least 3 hours before ECGs are obtained. ECGs must be obtained prior to the collection of any blood sample because drawing blood can affect the ECG. To standardize the collection procedure, the ECG should be collected in a comfortable and quiet place after the subject has been allowed to rest in a supine position for approximately 5 minutes.

All ECGs must be reviewed for safety at the site by a physician qualified to read and interpret the results (ie, a pediatric cardiologist, or an adult cardiologist experienced in the interpretation of pediatric ECGs should be contacted to discuss the ECG). This assessment will include the calculation of QTcF. ECGs must be reviewed on the day of the recording, signed and dated by the reader, and retained in the subject's study records.

ECGs in this study will be collected with an ECG recorder to be supplied to the site. This machine can generate a hard copy tracing, as well as digitally transmit via a modem to a central ECG service (BMS- BioMedical Systems). Standardized site and subject identification information have to be entered into the machine by the ECG technician prior to each recording. The electronic version transmitted to BMS will be the same as the hard copy. BMS will provide clinical interpretation and overread designated parameters (Heart Rate (HR), PR, Respiration Rate (RR), QRS QT, QTcF, QTcB).

ECGs showing a QTcF of ≥ 480 msec or a suspected increase from baseline of 60 msec or greater must be repeated within the same visit. If the QTcF value persists at ≥ 480 msec and/or the change from baseline persists at ≥ 60 msec, the study drug must be discontinued immediately and a pediatric cardiologist or an adult cardiologist experienced in the interpretation of pediatric ECGs should be contacted to discuss the ECG result.

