Centrally over read ECG variables will be summarized by mean change from baseline to each measurement time for heart rate, PR interval, RR interval, QRS width, QT interval and QTcB (Bazett's correction) and QTcF (Fridericia's correction) values. Additionally, the incidence of categorical increases in QTc intervals will be provided. Categories for QTcF and QTcB are ≥ 450 msec, ≥ 480 msec, and ≥ 500 msec. Categories for QTcF and QTcB as change from baseline are ≥ 30 msec increase, ≥ 60 msec increase and ≥ 75 msec increase. QTcF is considered the primary QTc value as this correction is more appropriate.

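### Schedule of Activities footnote e puts the on-treatment QTcF stop above 480 msec or above a 60 msec rise; Protocol 6.4 and 7.2 put it at those values

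*Protocol*

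**What the plan says.** The on-treatment QTcF rule has two steps, a repeat ECG at the same visit and then a stop if the finding persists. It appears in three places in the Protocol.

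- **Schedule of Activities, footnote e.** The repeat: "ECGs showing a QTcF of >480 msec or a suspected increase from baseline of 60 msec or greater must be repeated". The stop: "If the QTcF value persists at >480 msec and/or the change from baseline persists at >60 msec".
- **Section 6.4, Subject Withdrawal, Prolonged QT row.** The repeat is at QTcF ≥480 msec or a suspected rise of at least 60 msec. The stop: "If the QTcF value persists at ≥ 480 msec and/or the change from baseline persists at ≥ 60 msec". The row then treats "A verified increase in QTcF of ≥ 60 msec or a verified occurrence of QTcF ≥ 480 msec" as an adverse event of QTc prolongation.
- **Section 7.2, Electrocardiograms.** The repeat and stop have the same inclusive limits as 6.4.

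Three other places bear on how to read these. The introduction to the schedule calls it an overview and refers to the Study Procedures and Assessments "sections of the protocol for detailed information on each procedure and assessment required for compliance with the protocol". Section 9.3 plans inclusive summary categories: "Categories for QTcF and QTcB are ≥ 450 msec, ≥ 480 msec, and ≥ 500 msec". Exclusion criterion 1 in Section 4.2, which governs entry rather than treatment, uses strict limits: ">480 msec or increase from baseline QTcF >60 msec".

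**The concern.** Footnote e and the two body sections are meant to be one rule, but they use different operators. The footnote is attached to the ECG row of the visit schedule, where site staff may well look first, and it is worded as an instruction to stop drug at once. It is not worded as a pointer to another section.

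At stake is whether a subject whose reading lands exactly on a limit stays on ziprasidone. There is also a smaller point of event capture. At QTcF 480 msec with a rise below 60, a site working from the footnote need not repeat the ECG. The value may then never be verified, and the adverse event that 6.4 defines may not be recorded.

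**Working it through.** No sample size or error rate is involved. The check is to write out the two rules and see where they part. Let Q be QTcF in msec and R the rise from baseline in msec. Assume both are read in whole milliseconds; the documents do not state the recording precision.

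**The rules**

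- Footnote e: repeat if Q > 480 or R ≥ 60; stop if, on repeat, Q > 480 or R > 60.
- Sections 6.4 and 7.2: repeat if Q ≥ 480 or R ≥ 60; stop if, on repeat, Q ≥ 480 or R ≥ 60.

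**Test values (the repeat ECG gives the same reading)**

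| Q | R | Footnote e: repeat / stop | 6.4 and 7.2: repeat / stop |
|---|---|---|---|
| 479 | 59 | no / no | no / no |
| 480 | 40 | no / no | yes / yes |
| 460 | 60 | yes / no | yes / yes |
| 480 | 60 | yes / no | yes / yes |
| 481 | 40 | yes / yes | yes / yes |
| 460 | 61 | yes / yes | yes / yes |

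**Where they differ**

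- Repeat: only at Q = 480 with R < 60.
- Stop: only when Q ≤ 480 and R ≤ 60 with at least one of them on its limit, that is, Q = 480 with R ≤ 60, or R = 60 with Q ≤ 480.

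**Internal check of footnote e.** At R = 60 and Q ≤ 480 its repeat condition is met (R ≥ 60), but its stop condition cannot be met by a repeat giving the same reading (R > 60 fails). In 6.4 and 7.2 the repeat and stop limits coincide.

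**Which text to correct.** Sections 6.4 and 7.2 agree with each other, and they fall under the two chapters that the schedule names as holding the detail. Section 6.4 also ties its adverse event definition to the inclusive limits. Footnote e is the only on-treatment statement that differs.

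**The case against.** The strongest reply is that the Protocol already resolves the conflict. The schedule describes itself as an overview and defers to the body, and the mandatory withdrawal table in 6.4 is inclusive. A site that follows the body text stops the drug correctly. This stands as a limit on the harm: only a reader who relies on the schedule alone goes wrong, and only at an exact boundary. It does not make the footnote correct.

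A second reply is that exclusion 1 also uses strict limits, so the strict form may have been intended, and that the Section 9.3 categories are reporting bins that settle nothing about a stopping rule. The point about 9.3 is fair, and the conclusion does not rest on it. Exclusion 1 concerns entry, on findings from the preceding study, and no other text in these documents contradicts it. It does not explain why the footnote's repeat and stop limits differ from each other. It does, with the ≥45 kg printed correctly in nearby footnotes, make it unlikely that the sign in footnote e was simply lost in conversion of the file.

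A reader might also infer a larger QTc problem from the baselines. SAP 3.4 takes the A1281198 Baseline visit as ECG baseline for everyone. Protocol 9 uses, for prior-placebo subjects, the last observation before extension dosing. Section 7.2 says "Baseline ECG data will be obtained from A1281198 final study visit". It is tempting to conclude that the QTc change summaries are unsound, or that the counts of rises ≥60 msec ought to reconcile with site stops. The documents do not support either conclusion:

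- Protocol 9 allows the SAP to modify its plans, and SAP 3.4 states its ECG rule openly, so the analyst has one unambiguous definition.
- For prior-placebo subjects both candidate baselines precede any ziprasidone, so neither absorbs a drug effect.
- Site stops rest on a same-day site reading and persistence on a repeat. The summaries use centrally read values with no stated persistence requirement. The two would not match under any choice of baseline.

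**Conclusion.** Footnote e is wrong as written, and the point is minor. It conflicts with 6.4 and 7.2 on the stop at exactly 480 msec (rise no more than 60) and at a rise of exactly 60 msec (QTcF no more than 480). It conflicts on the repeat at exactly 480 msec with a rise below 60. Elsewhere the texts give the same action. The documents give no QTcF distribution, so the number of subjects likely to fall on a boundary cannot be estimated; about 55 are expected to be eligible for the extension.

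The conclusion rests on whole-millisecond readings and on the body text being the intended rule, which the schedule's own introduction supports. It does not extend to a claim that subjects are generally left unprotected, since a site following the withdrawal table acts correctly. The difference between SAP 3.4 and Protocol 9 in the ECG baseline for prior-placebo subjects is a side note and requires no change.

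**What to change.** In footnote e, change both QTcF limits (repeat and stop) to ≥480 msec and the persistent change from baseline to ≥60 msec. The repeat trigger for a suspected rise is already inclusive and stays as it is. Sections 6.4, 7.2 and 9.3 need no edit.

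The cost is one corrected footnote at the next amendment, with no new data, procedures, tables or analyses. Optionally, SAP 3.4 could carry a short cross-reference noting that its ECG baseline for prior-placebo subjects differs from Protocol 9; nothing in SAP 6.5.6 needs to change.
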